4.1 Additional Study Sites

No additional study sites.

5. Study Population

15 males with ED of organic origin and diabetes. All patients will be regular PDE5i users/responders. Men with ED will be evaluated by IIEF-EF domain and eligible patients will be enrolled in this open label pilot study. Participants who do not meet eligibility criteria will be considered a screen failure and will not receive the study therapy.

5.1 Inclusion criteria:

In order to participate in this study, a patient must:

- 1) Be Male.
- 2) Be 30 to 80 years of age (inclusive).
- 3) Be able to provide written informed consent.
- 4) Have a diagnosis of mild to moderate ED (12-21) or mild ED (22-25) based on IIEF-EF questionnaire score.
- 5) Have diagnosis of Diabetes Mellitus (Type 1 or Type 2) as documented by history of hemoglobin A1C > 7% OR on medical therapy for Diabetes.
- 6) Be in a stable relationship and have a minimum of 2 sexual attempts per month for at least one month prior to enrollment.
- 7) Agree to comply with all study related tests/procedures.

5.2 Exclusion criteria:

In order to participate in this study, a patient must not have any of the following:

- 1) Previous penile surgery of any kind (except circumcision and condyloma removal), such as penile lengthening, penile cancer surgery, penile plication, grafting.
- 2) Previous history of priapism, penile fracture, Peyronie's Disease, or penile curvature that negatively influences sexual activity.
- 3) Abnormal morning serum testosterone level defined as a value lower than 300 ng/dL (±5%).
- 4) Psychogenic ED as determined by study investigator.
- 5) Patients using ICI for management of ED
- 6) Patients with generalized polyneuropathy, neurological conditions, or psychiatric disease (such as bipolar disorder or depression).
- 7) Have a serious comorbid illness or condition that, in the opinion of the investigator, may compromise the safety or compliance of the subject or preclude successful completion of the study.
- 8) History of consistent treatment failure with PDE5 inhibitors for therapy of ED.
- 9) Poorly controlled diabetes as indicated by Hemoglobin a1c > 7.5%.
- 10) Use of antiplatelet medication.

6. Identification and Enrollment of Subjects

6.1 Recruitment and Pre-screening

The research coordination team may develop materials to aide in recruitment. This may include, but is not limited to, informational videos and brochures which provide education about erectile dysfunction and include information about the study; physician referral letter templates which can be used to promote awareness of the study in the urology community; flyers/posters which can be utilized at approved clinic locations and as part of health fair materials; templates for print advertisements which can be utilized in newsprint and media campaigns. Not all materials have been developed prior to trial initiation, however each of these recruitment methods will be reviewed and approved by the IRB prior to use.

Pre-screening of subjects includes reviewing medical records and imaging studies for inclusion/exclusions prior to consent. From the review of subjects' medical records and imaging studies on file, subjects who are determined to have a diagnosis of erectile dysfunction of organic origin and have mild-moderate erectile function as assessed by IIEF-EF, as stated in Section 5.1, and also do not have evidence in their medical record of study exclusions stated in Section 5.2, are eligible to be consented to the study.

Investigators will inform research staff of potential participants who have been identified through pre-screening so the subjects can be approached to discuss the study and conduct the informed consent session. No study procedures will take place prior to the subjects signing of the informed consent form.

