****CONFIDENTIAL & PROPRIETARY****

List of Abbreviations and Definition of Terms

AE	Adverse Events
BPH	Benign Prostatic Hyperplasia
BRB	Biomedical Research Building
CNS	Central Nervous System
CRF	Case Report Form
CTCAE	Common Terminology Criteria for Adverse Events
eCRF	Electronic Case Report Form
ED	Erectile Dysfunction
EDITS	Erectile Dysfunction Inventory of Treatment Satisfaction
EDV	End Diastolic Velocity
GCP	Good Clinical Practice
HIPAA	Health Information Portability and Accountability Act
ICF	Informed Consent Form
ICH	International Conference of Harmonization
ICI	Intracavernosal Injection
IEC	Institutional Ethics Committee
IIEF	International Index of Erectile Function
IIEF-EF	Erectile Function Subdomain Score
IRB	Institutional Review Board
ISCI	Interdisciplinary Stem Cell Institute
MCID	Minimal Clinically Important Difference
mL	Milliliter
ng/dL	Nanograms Per Deciliter
PDE5i	Phosphodiesterase 5 inhibitor
PPP	Platelet Poor Plasma
PRFM	Platelet Rich Fibrin Matrix
PRP	Platelet Rich Plasma
PSV	Peak Systolic Velocity
RCT	Randomized Controlled Trial
SAE	Serious Adverse Events
SEP3	Sexual Encounter Profile
SOP	Standard Operating Procedure
SWT	Low-intensity Shockwave Therapy
TE-SAE	Treatment Emergent Serious Adverse Events
UM	University of Miami
VAS	Visual Analogue Pain Scale

Protocol Synopsis						
TITLE	COMBINING SHOCKWAVE THERAPY AND PLATELET RICH PLASMA FOR TREATING ERECTILE DYSFUNCTION IN DIABETIC MEN (COCKTAIL-DM)					
SPONSOR	Jniversity of Miami, Miller School of Medicine - Department of Urology					
PHASE OF STUDY	Phase I/II					
STUDY THERAPY	Autologous Platelet-Rich Plasma (PRP) + Low-intensity Shockwave Therapy (SWT)					
STUDY DESIGN	Single arm, Open Label, Pilot Trial					
ROUTE OF ADMINISTRATION	Intracavernosal Injection (PRP) + extracorporeal shockwave therapy (SWT)					
SUBJECT POPULATION	15 male subjects between the age of 30-80 with Mild or Mild-to-Moderate ED and controlled Diabetes Mellitus (DM)					
STUDY	Primary: To investigate biochemical markers of neo-angiogenesis in patients before and after PRP injection + SWT					
OBJECTIVES	Secondary: To study efficacy and incidence of adverse events and safety of PRP injection + SWT treatment in men with mild-moderate ED, as measured by IIEF.					
	15 men with Erectile Dysfunction (ED) of organic origin and Diabetes (Type 1 or Type 2), that meet all of the inclusion and none of the exclusion criteria, will be enrolled and will receive PRP+SWT.					

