1.3 Energy-based treatments for erectile dysfunction

Shockwave therapy has been utilized by urologists for other ailments, such as treatment of kidney stones through a non-invasive manner. Interest in the use of low-intensity shockwave therapy for erectile dysfunction was augmented with success seen in preclinical models. The hypothesis for SWT's mechanistic actions is neo-angiogenesis, recruitment of progenitor cells and resident stem cells, improvement of microcirculation, vasodilation with subsequent increase in nitric oxide, decrease in fibrosis, and nerve regeneration. There have been 13 published clinical studies regarding use of SWT for ED. Multiple systematic reviews and meta-analyses have been performed for SWT for ED, and there is consensus that SWT shows promise in the treatment for ED.

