11.1 Adverse Events (AEs)

An adverse event (AE) is defined as any untoward medical occurrence associated with the use of a drug in humans, whether or not considered drug related. An AE can be any unfavorable and unintended sign (including an abnormal laboratory finding), symptom, or disease temporally associated with the study. The event does not need to have a causal relationship with treatment. Common Terminology Criteria for Adverse Events Version 5 (CTCAE) will be used for describing AEs. All urological and/or reproductive system AEs will be recorded. For all other AEs, only events greater than grade 2 will be recorded.

Based on our own pilot data assessing SWT and PRP monotherapy, we have compiled the following data on adverse events (Table 2):

We anticipate there to be few adverse events related to the study. Based on the four published studies and abstracts, including 75 men, only minor adverse events were reported (Bruising 1, Mild Pain 4). No serious adverse events were observed [23-26].

SWT related adverse events	
Transient mild cutaneous purpura	0.10%
Local erythema	0.50%
Local swelling/edema	1.00%
Transient local anesthesia or paranesthesia	1.10%
Transient local anestnesia of paranestnesia	1.10/0

PPR related adverse events					
Pain greater than 5/10 at time of injection	5.00%				
Pain lasting > 5 days	5.00%				
Penile bruising	0.00%				
Penile fracture	0.00%				

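### Earlier penile shockwave therapy or completed PRP is not an exclusion and no washout is set, so the baseline of a 15-man before/after comparison could already be treated

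*Combined protocol and SAP*

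**What the plan says.** **Eligibility.** The synopsis and Section 5.2 give the same ten exclusions. Those closest to earlier treatment are:

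- no. 1, earlier penile surgery, with lengthening, cancer surgery, plication and grafting as examples;
- no. 5, "Patients using ICI for management of ED";
- no. 7, a serious illness or condition that "may compromise the safety or compliance of the subject or preclude successful completion of the study";
- no. 8, "History of consistent treatment failure with PDE5 inhibitors for therapy of ED".

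None of the seven inclusion criteria in Section 5.1 asks for men who have not had SWT or PRP.

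**Source of patients.** Section 11.1 introduces its adverse-event table with "Based on our own pilot data assessing SWT and PRP monotherapy". Section 6.1 describes pre-screening from medical records against Sections 5.1 and 5.2, alongside brochures, referral letters, flyers and advertising.

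**Objective and mechanism.** The synopsis states the primary objective as "To investigate biochemical markers of neo-angiogenesis in patients before and after PRP injection + SWT". The primary markers in Section 3.1 include VEGF and endothelial progenitor cells (EPCs). Section 1.3 says: "The hypothesis for SWT's mechanistic actions is neo-angiogenesis, recruitment of progenitor cells and resident stem cells".

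**Baseline data.** Section 7.2.5 accepts a penile Doppler result from the preceding 12 months, and Section 7.2.6 an IIEF result from the preceding 6 months. The EPC colony count (Section 7.2.10) has no such provision and is scheduled at screening.

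**The concern.** A before/after comparison needs a baseline free of the treatment under study. As written, a man who had completed SWT or PRP before screening is not excluded for that reason. If earlier treatment acts through the mechanism that the protocol hypothesises, his marker levels at screening may still carry some of its effect. His change from baseline then combines the new treatment with the fading of the old one.

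A concurrent control group might show such drift. The synopsis and Section 7 describe a single open-label arm in which all 15 men receive both therapies. Section 12.1 has no covariate, subgroup or sensitivity analysis for earlier treatment.

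**Working it through.** **1. Does any provision close the gap?**

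| Provision | Current PRP | Completed PRP | Earlier SWT |
|---|---|---|---|
| Exclusion 1 (surgery) | no | no | no |
| Exclusion 5 (ICI use) | arguably | no | no |
| Exclusion 7 (serious illness or condition) | no | no | no |
| Exclusion 8 (PDE5i failure) | no | no | no |
| Medical history, 7.2.3 | recorded, no rule | recorded, no rule | recorded, no rule |
| Analysis plan, 12.1 | nothing | nothing | nothing |

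Exclusion 5 earns its 'arguably' because the abbreviation list defines ICI as intracavernosal injection, and the synopsis gives that as the route for PRP.

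**2. Direction of the bias.** Let τ be the effect of the study treatment in a given man, c0 the effect of earlier treatment still present at screening, and c1 what remains of it at follow-up. Assume the effects add and that c0 ≥ c1 ≥ 0. The documents give none of these values.

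- Baseline measured after the earlier treatment: observed change = (c1 + τ) − c0 = τ − (c0 − c1), so the new effect is understated.
- Stored baseline taken before the earlier treatment: observed change = (c1 + τ) − 0 = τ + c1, so the new effect is overstated.

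The first case applies to the EPC count, which is drawn at screening. The second can apply to Doppler (secondary) and IIEF-EF (exploratory). The same man could therefore bias different endpoints in opposite directions. For IIEF this arises only if a stored result is used, because Section 7.3.1 also has subjects complete the questionnaire at screening.

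**3. Weight of each man.** 1/15 = 6.7%. With k previously treated men, the bias in the cohort mean is k/15 times their average individual bias.

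**4. Illustration of size.** The documents give no effect size, standard deviation or power for N = 15, so there is no figure to reproduce. Assumptions: two-sided paired t-test, α = 0.05 (Section 12.1 gives α but not sidedness), n = 15. Power of 80% then requires a standardized change d = 0.78. Suppose k men, a fraction f = k/15, show no further change. The mean change becomes d(1 − f) and the SD becomes √(1 + f(1 − f)d²), in units of the original SD. For k = 2: f = 0.133, mean = 0.674, SD = 1.034, ratio = 0.652.

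| k | Fall in mean change | Power |
|---|---|---|
| 0 | 0 | 80% |
| 1 | 6.7% | about 73% |
| 2 | 13% | about 65% |
| 3 | 20% | about 57% |
| 5 | 33% | about 42% |

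This is a range over an unknown k under one assumed response pattern. It is not an estimate for this trial.

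**The case against.** The strongest reply is that harm depends on two unknowns: whether any previously treated man is enrolled, and whether an earlier effect persists. Section 1.3 states the SWT mechanism as a hypothesis. Section 1.4 rests the demonstrated effect on pre-clinical work and says that earlier human studies measured IIEF scores, Doppler parameters or both. The documents show neither a lasting human effect on EPCs nor its duration. This stands: carry-over is plausible, not documented.

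It is also fair that past history is taken at screening and concomitant therapy is recorded, so in 15 men at one institution prior exposure could be identified. But no rule acts on that information and no analysis uses it.

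Exclusion 5 may reach a man currently receiving PRP injections. That narrows the gap without closing it for completed PRP or for any SWT.

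Three stronger readings are tempting, and the documents do not support them.

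- *That the 0.10% SWT event rate in Section 11.1 implies a large local pool.* One event rounds to 0.10% only from 1/0.00105 = 952.4, so 953 units, if the rates are exact to two decimals. Every listed rate ends in zero, which fits one-decimal values padded to two, and then 1/0.0015 = 666.7, so 667, would do. The unit (men or sessions) is not stated, and nothing shows how many of them would be eligible here.
- *That former pilot participants are the likeliest recruits, or would meet all criteria.* Section 11.1 does not say where or when they were treated, whether they were diabetic, or whether they would be approached. Section 6.1 lists other recruitment routes. Such men would still have to satisfy every other criterion.
- *That prior exposure spoils the separation of combination from monotherapy.* A single arm cannot make that separation even in men never treated before.

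Sections 7.3.2, 8.1, 8.2.1 and 12.1 do refer to randomization or a control group. The point here follows the synopsis and Section 7, which describe one arm.

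**Conclusion.** The omission is real. Neither eligibility list addresses earlier penile SWT or completed PRP, no washout is stated, and nothing elsewhere in the plan compensates. The consequence is conditional: the baseline could already be treated, and the documents do not show that it will be. Each affected man carries 6.7% of a comparison that has no control group to reveal the problem. Two such men would lower the mean change by 13% if they showed no further change, which is an assumption about both their number and their response. The direction can reverse for Doppler or IIEF-EF where a stored result predates the earlier treatment; the primary EPC measure is not exposed to that reversal. This is a specific, inexpensive improvement to the design, not evidence that the trial's result is invalid.

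**What to change.** Add one exclusion to Section 5.2 and the synopsis: previous penile shockwave therapy or intracavernosal PRP, including in earlier studies. Confirm it from the history already taken at screening.

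If the sponsor prefers to keep such men, four changes are needed instead:

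- set and justify a minimum interval since last exposure (the length is for the sponsor to determine);
- record the type and date of prior exposure on the case report form;
- require any stored Doppler or IIEF result used as baseline to postdate that exposure;
- state in Section 12.1 that the primary result will be reported with and without exposed men.

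The first option costs one criterion and perhaps a few candidates. The second keeps those candidates, but needs extra data fields and an added analysis in an already small sample.

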3.1 Primary Endpoints

- Changes in markers of vasodilation (eNOS, nNOS), neo-angiogenesis (VEGF, CD-31), and systemic markers of endothelial function (EPCs, SDF-1α, and SCF).

3.2 Secondary Endpoints (efficacy):

- Differences in Doppler ultrasound parameters (PSV and EDV) from baseline to 6 months post-therapy.
- Treatment satisfaction as assessed by EDITS questionnaire in all subjects.
- Incidence of Serious Adverse Events experienced up to 6 months post-therapy.

3.3 Exploratory Endpoints:

- Change in IIEF-EF score from baseline to 3 and 6 months post-therapy.
- Percentage of subjects that achieve minimal clinically important difference (MCID) in IIEF-EF from baseline to 3 and 6 months post-therapy.
- Percentage of subjects who either decrease or discontinue use of PDE5i after three months post-therapy

4. Study Location

The study will be funded by the CTSI pilot award (GR019191) and coordinated by the University of Miami (UM), Miller School of Medicine, Desai Sethi Urology Institute. All

study visits will take place in the Department of Urology clinics, (PAC: [name], University of Miami Miller School of medicine, Miami, FL. & Lennar: [name]) PRP preparation and SWT therapy administration will take place in the PAC andrology lab and clinic.

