6.4 Withdrawal Criteria

All subjects who either screen fails, is withdrawn from the study, or has completed all visits should be de-enrolled from the research database within 2 business days, in accordance with university policies (or respective institutional policy).

Subjects may be withdrawn from the study for any of the following reasons:

- a) A subject does not meet the eligibility criteria (the subject will be considered a screen failure).
- b) A subject withdraws consent.
- c) A subject expires during protocol participation from causes other than the study treatment (not due to adverse events).
- d) At the discretion of the principal investigator for issues of non-compliance, or other behavioral factors.

7. Procedures Involved

15 men with Erectile Dysfunction (ED) of organic origin, that meet all of the inclusion and none of the exclusion criteria, will be enrolled to receive PRP+SWT in an open-label fashion.

Autologous PRP injection + SWT therapy. All subjects in this group will receive 2 sessions of autologous PRP penile injection with 28 ± 2 day treatment interval. 5mL of PRP will be injected at each session. Additionally, patients will receive a total of 3600 shocks over a five-week period, starting at initial PRP injection.

7.1 Schedule of Events:

-

The events table for the conduct of this study is shown below:

Table1:

Schedule of Events		Screening			Follow Up				
Time Point		0-30 days	Week 0	Week 1	Week 2	Week 3	Week 4	Month 3	Month 6
Eve	nt	before randomization	Day 0	Day 7 ± 2	Day 14 ± 2	Day 21 ± 2	Day 28 ± 2	Day 90 ± 14	Day 180 ± 14
Infor	med Consent	x							
Dem	ographics	x							
Medi	cal History	x							
Phys	ical Exam	x							
Dopp	oler Ultrasound	x							X
aires	IIEF	x						X	x
tionna	EDITS							X	x
Ques	VAS		x	x	x	x	x		
Labo	ratory Tests*	x							
EPC	-CFUs	X						X	Х
Brac	hial FMD	X						Х	Х
PRP Injection			х				х		
Shockwave Therapy			Х	Х	Х	Х	Х		
Concomitant Medications/Therapy		x	x	х	х	x	x	x	x
Review Adverse Events			х	x	x	x	х	x	x

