- **7.2.13** *Shockwave Therapy (SWT)*: In the treatment group, patients randomized will receive 5 weekly sessions, in which 720 shocks of treatment energy will be applied in every session to each treated region (left and right corpora cavernosa and crura) for a total of 3,600 shocks. Refer to Section 8 for description of Investigational Product (IP) preparation and administration.
- **7.2.14** *Concomitant Medications:* Review of current use of prescription and over the counter (OTC) medications. Participants must discontinue use of PDE5i medications throughout the duration of the study.
- **7.2.15 Review Adverse Events:** Refer to Section 11 for description and reporting of adverse and serious adverse events

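### Scores obtained on another ED treatment count as PRP+SWT results: the plan has no rule for PDE5i, ICI, device or other ED aid used before Month 3 or Month 6, and contradicts itself on PDE5i use

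*Combined protocol and SAP*

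**What the plan says.** - **Design.** The synopsis describes a "Single arm, Open Label, Pilot Trial", and section 5 sets the population as "15 males with ED of organic origin and diabetes".
- **ED treatment at entry.** Section 5 adds "All patients will be regular PDE5i users/responders". Exclusion 5 in section 5.2 rules out "Patients using ICI for management of ED". It is an eligibility rule, and nothing extends it into follow-up.
- **ED treatment on study.** Section 7.2.14 states "Participants must discontinue use of PDE5i medications throughout the duration of the study". No other ED treatment is restricted after entry. Section 6.4 does not list starting one as a reason for withdrawal; the nearest item is investigator discretion over non-compliance.
- **Recording.** The schedule in 7.1 has a row "Concomitant Medications/Therapy", marked at every visit including Months 3 and 6. The text in 7.2.14 describes it as "Review of current use of prescription and over the counter (OTC) medications", which does not mention devices.
- **Endpoints.** Section 3.2 lists "Treatment satisfaction as assessed by EDITS questionnaire in all subjects". Section 3.3 lists IIEF-EF change and the share reaching MCID at 3 and 6 months, and also the share of men who cut down or stop PDE5i beyond three months after therapy.
- **Baseline.** Section 7.2.6 allows an IIEF completed in the previous 6 months to be used.
- **Analysis.** Section 12.1 is one paragraph: repeated-measures ANOVA or t-test, and Fisher's exact test, at α = 0.05. It has no rule for other ED treatment.

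**The concern.** Men who respond to PDE5i are told to stop it for the whole study. Those who get little from PRP+SWT have the most reason to turn to something else, which could be an injection, a device or PDE5i again. If they do, their Month 3 or Month 6 questionnaire reflects that treatment, yet the plan analyses it as change after PRP+SWT. EDITS has the same problem: section 7.2.7 describes it as measuring satisfaction with medical ED treatment, and nothing ties the answer to PRP+SWT.

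A concurrent control arm would offset at least part of this. There is none. At stake is whether the MCID rate, mean IIEF-EF change and EDITS can be read as effects of the study therapy.

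**Working it through.** The documents give no power calculation, SD, MCID value or expected use of other ED treatments, so there is no planned figure to reproduce. The check has three parts.

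**1. Reading the rules together**

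| Question | Text | Answer |
|---|---|---|
| May a man start ICI, a device or another aid after Day 0? | 5.2(5), 6.4, 7.2.14 | Not addressed |
| May he use PDE5i in follow-up? | 7.2.14 against 3.3 | Barred in one, presupposed in the other |
| Would use be recorded? | 7.1 row; 7.2.14 | Drugs yes; devices unclear |
| Does the analysis act on it? | 12.1 | No |

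The endpoint on reduced or stopped PDE5i use does need concomitant-medication data. But nothing links that information to how an IIEF-EF or EDITS score is counted. A score obtained on another ED treatment therefore enters as observed.

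**2. Size of the contribution**

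Input from the documents: n = 15. Assumed: k men use another treatment, and each gains g IIEF-EF points from it.

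- Rise in MCID rate: at most k/15, reached only if none of the k men would have met MCID anyway. One man: 1/15 = 6.7 percentage points.
- Rise in mean IIEF-EF change: k × g/15. For example, 3 × 4/15 = 0.80 and 3 × 8/15 = 1.60.

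For scale, 100,000 simulated trials were run per setting with no true PRP+SWT effect. Each used a two-sided one-sample t-test on change at α = 0.05. That test is an assumption, since 12.1 describes a between-group comparison that a single arm cannot supply. Also assumed: g of 4, 6 or 8 points, and an SD of change of 4 or 6.

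| k | MCID rate, up to | Mean change, g = 4 to 8 | Chance of a significant apparent gain |
|---|---|---|---|
| 0 | 0 | 0 | 2.5% (nominal) |
| 1 | 6.7 points | 0.27 to 0.53 | 3.4% to 4.5% |
| 2 | 13.3 points | 0.53 to 1.07 | 4.7% to 8.0% |
| 3 | 20.0 points | 0.80 to 1.60 | 6.0% to 13.9% |
| 5 | 33.3 points | 1.33 to 2.67 | 10.5% to 36.9% |

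With one or two users the effect is modest; with five it is substantial. These are ranges over assumptions, not estimates for this trial.

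**3. Direction of the net bias**

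A second mechanism can work the other way. If the baseline IIEF was completed while a man was on PDE5i, stopping PDE5i may lower his later scores. Let L be the average loss over all 15 men from this cause. The net bias in mean change is then k × g/15 − L. With k = 3 and g = 6 the first term is 1.20, so the sign turns negative once L exceeds 1.20 points. The documents give neither L nor the number of men whose baseline was obtained on PDE5i, so the sign cannot be settled.

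**The case against.** **The affected endpoints are minor.** IIEF-EF and MCID are exploratory, EDITS is one of several secondary measures, and the primary endpoints are biomarkers in a 15-man pilot with no success criterion. This stands and limits the severity. It does not remove the point: EDITS is a listed secondary endpoint, and the synopsis words its secondary objective as efficacy measured by IIEF.

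**Use of other treatments is speculative.** No rate is given, the vacuum device appears only in a small cited rehabilitation study, and men with low testosterone are excluded. This stands as a limit on the numbers. The most obvious candidate, however, is PDE5i itself in men who are regular users, and section 3.3 envisages its use.

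**Safeguards exist.** Concomitant treatment is reviewed at every visit, and the investigator may withdraw a non-compliant man. The review makes drug use visible but does not change how a score is counted. Withdrawal is discretionary and does not name this case.

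**Stronger readings that the documents do not support:**

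- A reader might infer that results are biased upward overall. Only the contribution of other treatment is upward; the age and PDE5i status of the baseline leave the net direction open.
- A reader might infer that exclusion 5 contradicts 7.2.14. It does not: one governs entry and the other on-study medication. The gap between them is an omission. The actual contradiction is between 7.2.14 and the PDE5i endpoint in 3.3.
- A reader might infer that the concomitant-treatment record serves no endpoint. The PDE5i endpoint needs such data.

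**Conclusion.** The point holds in a limited form. Exclusion of ICI applies at entry only, PDE5i is the sole ED treatment restricted afterwards, and the plan is inconsistent on whether PDE5i may be used in follow-up. Section 12.1 gives no way to separate scores obtained on another ED treatment, and there is no control arm. Any effect of such treatment is therefore attributed to PRP+SWT in the MCID rate, IIEF-EF change and EDITS.

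The one figure that rests on the documents alone is the 1/15 weight of each man: up to 6.7 percentage points of MCID rate, if he would not otherwise have reached it. Everything beyond that depends on assumed use, gain and SD. Severity is minor to moderate, and the primary biomarker endpoints are not part of this point.

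**What to change.** 1. Reconcile 7.2.14 with the PDE5i endpoint in 3.3, and state which ED treatments may be used after entry. What is allowed is the sponsor's clinical decision.
2. Make the existing concomitant-treatment record cover every ED treatment, including devices and PDE5i, with start and stop dates. An explicit question at Months 3 and 6 would do.
3. In 12.1 and 3.3, count a man who used another ED treatment within the IIEF assessment window as an MCID non-responder at that visit. Define that window, and say explicitly how PDE5i falls under the rule.
4. Report IIEF-EF change and EDITS with and without data obtained on such treatment. Do not set the change to zero: if the untreated change would have been negative, zero flatters the therapy, and a constant in place of a varying outcome can shrink the SD in a 15-man paired test.
5. Record whether each baseline IIEF was completed on PDE5i.

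The cost is a few sentences in the analysis plan, a short addition to the case report form and a little more analysis. The downside is a possibly less favourable MCID rate.
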